4.2 Preliminary Data and/or Findings

The safety of ReCell has been demonstrated with over 5,000 treatment procedures conducted worldwide. ReCell has CE Marking in Europe, TGA clearance in Australia, SFDA clearance in China and Health Canada approval as well as approval in other markets (e.g., Taiwan, Hong Kong, Mexico, Brazil and Venezuela). Case series studies include an 81-patient Australian study (PSR-01 and PSR-02) of epidermal replacement due to acute superficial skin injury, unhealed donor site, raised scars, or correction of hypopigmentation caused by a previous injury or skin resurfacing procedure. These studies included both pediatric and adult patients. Effectiveness assessments included: percent re-epithelialization through 6 weeks post-treatment, clinical assessment of wound appearance at recipient site (e.g., healed, not healed), assessment of skin quality by a blinded assessor (photography assessment) in terms of color match with the surrounding skin, pigment and texture at recipient site, and appearance of scar at donor site in terms of color, pigment and texture and degree of scarring. In both studies, minimum follow-up was 26 weeks post-treatment. Safety was assessed based on adverse events, vital signs and concomitant medication. All wounds achieved healing ($\geq 95\%$ re-epithelialization) by Week 6. At the final assessment (Week 52 for PSR-01 and Week 56 for PSR-02), no wounds were determined to be grossly mismatched to the surrounding area with respect to color, pigment, or texture. Within these studies, use of the ReCell device in epidermal restructuring was well tolerated and did not show any systemic effect. There was no association with any alteration in vital signs. Overall the safety profile of ReCell kit observed in these studies demonstrated that the ReCell device can be used in patients requiring epidermal restructuring without causing any systemic toxicity.

Furthermore, several recent publications report on positive clinical results with ReCell in a variety of indications, including deep partial thickness burns [Gravante G, et al., 2007], vitiligo [Mulekar SV, et al., 2007] and hypopigmented scarring [Goodman GJ, 2008, Cervelli V, et al., 2009, Draaijers LJ, et al., 2004].

To date, there is no preliminary data applicable for this indication. However, ReCell is currently being evaluated in the United States as a primary treatment of partial-thickness burns compared with standard split thickness meshed skin grafts in a multi-center clinical trial and at Wake Forest School of Medicine, Institute for Regenerative Medicine under the direction of [name], Medical Advisor for this proposed clinical trial. Safety monitoring of adverse events reveals application of the ReCell device has been well-tolerated and there have been no adverse events which are inconsistent or unexpected for the subject population.

4.3 Scientific Justification and Military Relevance

Significant soft tissue losses due to blast injuries are becoming more common in modern warfare. The efforts to manage these wounds are becoming more challenging. More than half of the injuries in modern combat are due to explosions; including mortars, rockets, and IEDs. The majority of these injuries are to the extremities, resulting in significant soft tissue loss and the need for available autologous skin sources. Given the complex and massive soft tissue injuries that traumatic blast injuries cause in a number of our wounded warriors, improved availability of skin regenerative techniques and methods to not only expand autologous skin donor sources but also to aid in lessening donor site morbidity is of great interest and importance. The ReCell Device is a stand-alone, battery operated regenerative skin cell separation device that enables preparation of a cell suspension from a small, thin, split-thickness skin biopsy site, thus, providing for great expansion of a limited autologous skin donor site.

Additionally, because the autologous epidermal cell suspension is available for immediate delivery onto a prepared skin surface at the time of skin donor harvest, the need for further cell expansion within the laboratory setting is avoided. The performance of ReCell over INTEGRA™ MBWM in combination with 1:5 meshed split-thickness skin graft (STSG) will be compared to standard practice control (i.e., 1:1.5 meshed STSG over INTEGRA™ MBWM), with the ultimate potential benefit of earlier re-epithelialization, acceptable durability, and reduction in the risk of infection and scarring for those wounds treated with ReCell.

Based on preclinical and early clinical results, the short-term benefits of this study will include potential viable and readily available regeneration of necessary autologous skin to place on a dermal regenerate in massive soft tissue injuries. This clinical model would be the first to potentially show the benefit of such treatments in traumatic wounds, outside of burn patients. It would also have immense benefits - both for those military healthcare beneficiaries suffering from soft tissue injuries as well as traumatic civilian injuries that likewise pose significant issues with available autologous skin coverage (e.g. necrotizing fasciitis, motor vehicle accidents or other trauma with associated soft tissue avulsion injuries, etc.). Important data on the mechanism of action, refinements of technique, expansion of the device and technique to future applications, and most importantly, technology transfer throughout WRNMMC, associated military treatment facilities (MTF), and civilian or academic centers is of great interest.

We expect all ReCell treated and control areas of the wounds to heal adequately. However, we hypothesize areas treated with ReCell will re-epithelialize more quickly than control areas, which has the potential to reduce the risk of infection and scarring in ReCell treated areas compared to control areas. Healing will be defined as: 95% or greater re-epithelialization has occurred at area treated by Week 6 post-treatment.

4.4 Human Subjects Justification.

The proposed prospective, non-randomized, within-patient controlled feasibility study will enroll 20 military healthcare beneficiaries, both male and female, currently

receiving treatment for a traumatic wound injury at WRNMMC. The goal of this study is to evaluate the safety, tolerability, preliminary and long-term effectiveness of the ReCell device for re-epithelialization of full-thickness wounds treated with INTEGRA™ MBWM.

Data collected in the completion of the proposed study will support or refute the hypothesis that the use of the ReCell device over a widened STSG mesh in combination with INTEGRA™ MBWM will improve upon the current standard of care for treating full-thickness wounds within the traumatic injury population. We believe that ReCell will promote improved healing within the interstices of finely meshed STSG, thus improving durability among STSG gaps that are potential points of failure during later physical activity.

Furthermore, ReCell will reduce the burden of donor skin graft sites by decreasing the amount of autologous skin grafting harvest necessary to cover massive soft tissue. In effect, we propose by using the existing standard for dermal regenerate in INTEGRA™ MBWM, full thickness wounds will be converted into partial thickness wounds, which can then be covered with finely meshed STSG and ReCell regenerative skin expansion system to provide more durable stable skin coverage while also reducing donor site morbidity and pain.

The impact of scar complications (i.e. pain, itching and fragility), may have impact on the quality of life. For the patient, the presence of pain and itching is often more disturbing than the actual appearance, and therefore these symptoms have a major impact on the quality of life. Additionally, scar formation can result in disabilities that impact activity levels for some.

Leveraging from prior experiences and successes of using ReCell within burn patients, this model will be the first to explore and allow for treating massive soft tissue injuries in a true traumatic setting. The results of the study will be presented at national meetings geared toward audiences that provide care to similarly injured individuals.

5. PLAN

5.1 Study Design

This is a prospective, single-center, randomized within-patient controlled feasibility study to evaluate safety, tolerability, preliminary and long-term effectiveness of the ReCell device when used in combination with STSG mesh for healing of full-thickness wounds previously treated successfully with INTEGRA™ MBWM. Due to the nature of the study, only patients whose wounds have been treated with INTEGRA MBWM as part of their standard of care will qualify for study participation. The local standard of care is considered the application of INTEGRA MBWM after the wound is amenable. Amenable being no evidence of evolving necrosis, clean and devoid of infection. The INTEGRA is allowed to mature until it takes (adheres) to the underlying tissue, which takes 2 to 4 weeks until the wound is amenable for split thickness skin grafting. Therefore, before consenting and enrollment into the study, the wound area to be studied will be treated first with INTEGRA™ MBWM then be allowed to heal for approximately two to four weeks (consistent with standard of care), at which time an assessment will be made to

determine if a viable granulation layer suitable for second stage grafting is present.
(Note: At this time the patient will complete the consent process as described below in Section 5.5.2).

The basic study design has the following characteristics:

- Each subject will serve as his/her own control
- After INTEGRA™ MBWM treatment (and once viable granulation is present), the study wound area will be divided into two regions within itself. Study treatment to each of the two regions will be assigned by randomization. Subjects will be blinded to treatment area assignments to avoid bias
- Each subject will be treated with meshed STSG over both the control and ReCell regions of the Integra-treated wound. The control area will have standard 1:1.5 meshing (only) STSG, and the experimental area will have 1:5 meshing STSG plus application of ReCell (ReCell will be applied over the 1:5 meshed STSG).

Once harvested, a STSG may be meshed by placing the graft on a carrier and passing it through a meshing device. A skin graft may be meshed to provide coverage of a greater surface area at the recipient site, with expansion ratios generally ranging from 1:1 to 6:1. This also allows for expansion of the donor skin to be grafted/transferred and permits egress of serous or sanguineous fluid from under the graft; however, it results in a pebbled appearance upon healing that may ultimately be of poorer cosmesis.

[figure not shown]
The carrier has a grooved side that must be directed superiorly and upon which the graft should be laid out. This technique allows expansion of the graft surface area up to 9 times the donor site surface area. Expansion slits allow wound fluid to escape through the graft rather than accumulating beneath the graft and preventing adherence. To create a meshed graft, a “mashing” apparatus (Zimmer, Padgett, and/or Bryan meshing systems) is used to put open spaces in the STSG in an organized fashion. This expands the graft so it can cover a larger surface area. The difference in ratios determines the expansion of the skin graft. For example, a 1:1.5 ratio has open spaces that are one and a half as large as the skin and a 1:5 ratio has open spaces that are five times as large as the skin. The larger the meshing ratio, the larger the surface area that can be covered by the graft.

[figure not shown]
a.

b.

c.

d.

e.

- a. Zimmer Dermatome utilize to harvest the split thickness skin graft. The thickness and width of the harvested graft can be adjusted.
- b. Dermatome blade width to determine the width of the harvested graft.
- c. Harvested split thickness skin graft
- d. Graft mesher
- e. Recipient site grafted.

Treatment Summary Table:

ReCell Region (experimental)	Control Region (standard of care)
ReCell + 1:5 Meshed STSG	1:1.5 Meshed STSG (no ReCell)
INTEGRA™ MBWM	INTEGRA™ MBWM
Wound Bed	Wound Bed

Allocation of treatments (Recell vs Control) to the INTEGRA™ MBWM treated wound sites will be assigned at random using a computer generated randomization table assignment to the two defined wound regions. Wound regions will initially be labeled A region and B region by the surgeon, and then the subject assigned randomization envelope will be opened to determine which of the two treatments will be used at A region and which treatment will be used at B region.

The wound area to be followed in the study will be between 200cm² and 640cm². One ReCell kit is intended to treat up to 320cm² (which will cover half of the total “maximum” 640cm² wound area), allowing for comparison with a similar size control area of up to 320cm² that is treated according to the standard of care.

In all cases, the ReCell region may be up to 320cm² in size, the upper limit of application area for one ReCell kit, with a similarly sized control region. If the wound is larger than the combined control and ReCell regions (over 640 cm²), areas outside the study regions will be designated non-study areas and treated according to the standard of care. Additionally, areas with incomplete granulation, defined as a contiguous vascularized granulation layer at the INTEGRA™ MBWM application site, will be excluded from the study wound area.

The same primary and secondary dressings will be used on ReCell-treated areas, control areas and donor sites. Once the wounds are determined to be healed, standard local clinical practice will be followed.

In order to evaluate improvements associated with use of ReCell, within-subject comparisons across a battery of measurements and evaluations will be made. These measurements are divided into three categories:

- Safety and tolerability measures
- Preliminary effectiveness (acute healing phase)
- Long-term effectiveness

5.2 Anticipated Requirements

Study procedures will be performed at WRNMMC within the following areas: In a private room within the Orthopaedic Surgery and/or Plastic Surgery Service clinic (screening and most post-operative visits), WRNMMC laboratory, WRNMMC Radiology, WRNMMC Dermopathology, WRNMMC Biomedical Research Laboratory (BRL) (obtainment of liquid nitrogen), WRNMMC Peri-Operative Services and surgical ward (Note, as per standard of care for surgical procedure and recovery) and utilization of the WRNMMC Investigational Pharmacy Services and the WRNMMC Information Technology (IT) Services (CHCS, Essentris and AHLTA) for conducting medical record review. Study procedures being performed at/by non-WRNMMC include: The collective monitoring activities intended to assess the investigator’s compliance with the protocol, the signed agreement, IRB requirements, and applicable FDA regulations in an effort to ensure human subject protection will be performed by IMARC, Inc. Under the supervision of [name] (Sponsor and holder of the IDE), study data will be housed at UPMC and the Center for Innovation in Restorative Medicine (CIRM) will serve as the data management center. [name] will maintain oversight regarding regulatory requirements and compliance of clinical data and data analysis. In collaboration with [name], coded data will be shared with Glaser Consulting who will perform all statistical analysis of data. Examination of cellular properties of the biopsy tissue material obtained from each subject by a member of the study team to determine skin composition relative to normal skin will be sent to and processed by an outside laboratory facility, Annapath, Inc. They in turn will ship slides back to WRNMMC to be interpreted by WRNMMC’s dermatopathologist, [name].

The study design consists of screening pre-treatment/baseline assessments, an acute

phase and a long term follow-up phase. The acute phase duration is 6 weeks subsequent to treatment with INTEGRA™ MBWM and post treatment with the ReCell device. Subjects will continue to be followed for up to 24 weeks to capture long-term outcomes. The total duration of the subject's participation in this research study across all visits, including screening and follow-up surveillance is expected to be up to 26-28 weeks.

The time required to complete the research (including data analysis)

Anticipated Start Date: May 2014

Expected Completion Date: Oct 2017

Budget and Source of Funds

Please see Appendix K for copy of budget

Funding will be provided by the United States Army Medical Research Acquisition Activity (USAMRAA) under Grant # W81XWH1320004

5.3 Subject Population

The research population to be studied will include male or female military healthcare beneficiary of any race or ethnicity, aged 18 years or older, who is being treated for a traumatic wound at WRNMMC. With a target enrollment of 20 evaluable subjects, this investigation will include individuals treated for traumatic wounds at WRNMMC with full-thickness wounds, with loss of the dermis extending to deeper tissue layers and disrupting dermal blood vessels, and deep partial-thickness wounds, with injury limited to the epidermis and superficial dermis with no damage to the dermal blood vessels that were successfully treated with INTEGRA™ MBWM. Successful INTEGRA™ MBWM engrafting is defined as the presence of a contiguous vascularized granulation layer.

It is planned to enroll a sufficient number of subjects at WRNMMC in order to ensure a total number of 20 evaluable subjects. Therefore, up to 30 subjects will be consented and enrolled then screened to achieve a maximum of 20 evaluable subjects. Subjects who do not receive treatment with the assigned study device (ReCell) will be considered non-evaluable and therefore a screen failure for study participation.

WRNMMC will be the coordinating center for this clinical trial and will be the only site to enroll subjects for participation. The University of Pittsburgh, UPMC Center for Innovation in Restorative Medicine (CIRM), under the direction of Dr. [name] will be the Sponsor of the IDE and will also function as the Data Coordinating Center (DCC) accountable for maintaining oversight of all data management activities to ensure quality and integrity with accurate reporting, interpretation and verification, and will ensure systems and procedures are in place for the protection and safeguarding of the confidentiality of all data records.

It is anticipated the availability of the study population will be derived from the investigators' clinical practices, individuals evaluated and/or referred by healthcare providers aware of the study within the WRNMMC Orthopaedic Surgery, Plastic Surgery and General Surgery Clinics. Additionally, study participants will be recruited by use of a posting on the research registry at www.clinicaltrials.gov. Those interested

in study participation will be instructed to contact a study team member. This study will not use any advertisements, flyers or brochures.

5.4 Subject Inclusion and Exclusion Criteria

a. Inclusion Criteria

Subjects will be eligible for study participation if they meet all of the following criteria:

- The subject is a male or female military healthcare beneficiary of any race or ethnicity, aged 18 years or older, who is being treated for a traumatic wound at WRNMMC
- The subject has soft tissue loss resulting from a traumatic mechanism such as an explosive blast (i.e. mortar, rocket, IED), high-velocity shells (i.e. missile), an avulsion injury, gunshot wound motor vehicle accident and/or burn secondary to blast
- The subject's full-thickness or deep partial-thickness traumatic wound injury has been treated with INTEGRA™ MBWM as part of their standard of care
- The wound area is at least 200 cm²
- All areas of the study wound area are covered with INTEGRA™ MBWM and has fully engrafted – engrafting defined as the presence of a contiguous vascularized granulation layer indicated by the formation of a viable granulation layer (**Note:** there may be some areas of incomplete granulation at the INTEGRA™ MBWM application site, these areas will be excluded from the study wound area).
- The subject will comply with protocol requirements
- The subject will provide voluntary written informed consent and Health Insurance Portability and Accountability Act (HIPAA) authorization

b. Exclusion Criteria

Subjects will not be eligible for study participation if they meet any of the following criteria:

- The subject is pregnant and/or lactating (self-reported)
- The subject has evidence of the following lab value results:
 - a. Hematocrit \leq 20%
 - b. INR $>$ 1.8 second
 - c. Creatinine (serum) $>$ 2.0 mg/dL
 - d. Bilirubin Total (serum) within upper limit of normal (normal range 0.3-1.9 mg/dL)
 - e. Liver function test (AST/ALT) greater than 2 times upper limit of normal as defined by the clinical laboratory defined normal ranges
 - f. Albumin (serum) $<$ 2.0 g/dL
 - g. Platelets $<$ 70 K/ μ L
- The subject's targeted traumatic wound injury is a craniofacial wound

- The subject's targeted traumatic wound injury is on a weight-bearing surface
- The subject's targeted traumatic wound is a full-thickness burn injury with visible eschar present (Note: Subjects with a traumatic wound of a burn nature secondary to an explosive blast injury resulting in significant soft tissue loss **will NOT** be excluded)
- The subject has active infection processes, that in the opinion of the investigator may compromise safety or study objectives
- The subject is known to have a pre-existing condition that may interfere with wound healing, e.g. malignancy, diabetes or autoimmune disease, immunocompromised blood borne diseases, has AIDS, is HIV or Hepatitis-A positive, or currently has a severe dermatological disorder (e.g. severe psoriasis, epidermolysis bullosa, pyoderma gangrenosum)
- The subject has other concurrent conditions that in the opinion of the investigator may compromise safety or study objectives
- The subject has a known hypersensitivity to Trypsin and/or Compound Sodium Lactate for Irrigation (Hartmann's) solution
- The subject cannot be compliant with study procedures and that, in the investigator's opinion, would interfere with the study objectives

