An evaluation of the traumatic wound area treated with INTEGRA™ MBWM will be made and recorded on the eCRF. The total wound area will be measured. The wound area will be inspected to ensure all areas of the study wound has fully engrafted as indicated by the formation of a viable granulation layer as this will allow for grafting. Both of these findings will be recorded on the eCRF.

A baseline assessment for heterotopic ossification will be established using radiographic imaging. Anterior/posterior and lateral films of the wound area targeted for treatment will be obtained. If the subject's medical record contains an x-ray taken of the wound area targeted for treatment within 30 days prior to enrollment indicating the presence or absence of heterotopic ossification, these radiograph images (x-rays) may be used to avoid unnecessary exposure to radiation.

A baseline assessment for pain and pruritus at the traumatic wound site will be obtained for comparison after receiving study treatment with ReCell. Subjects will be asked to rate their pain using a 0-10 point verbal numerical rating scale where "0" equals no pain and "10" equals worst pain possible. Additionally, the subject will be questioned if experiencing pruritus at the targeted wound site. If so, he/she will be asked to rate the intensity using the following options: mild, moderate and severe. Responses from both assessments will be recorded on the eCRF.

A blood sample (15 mls) will be drawn for hematological analysis including a complete blood count (CBC) with differential panel, coagulation studies to include prothrombin time (PT) and international normalized ratio (INR) and comprehensive metabolic panel (CMP). Results will be reviewed by a physician investigator and documented on the eCRF.

The total time of participant commitment for this portion of the screening pre-treatment baseline assessments including the consenting process will take approximately 1.5 to 2 hours.

Each subject must meet all inclusion and no exclusion criteria in order to qualify for receiving treatment using the ReCell device. The PI or designee will make the final determination of subject eligibility. Subjects who sign the informed consent/HIPAA authorization document, but do not meet eligibility criteria will be defined as a screen failure. The investigator will maintain a screening log that documents the subject ID number and reason(s) for screen failure.

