Tabulation of demographic data will be tabulated by age, gender and race/ethnicity.

Study Termination Analysis

The following analysis will be provided pertaining to Study Termination:

- Number and percent of subjects who completed the study
- Frequency of premature termination reasons
- A listing of all subjects who were prematurely terminated from the study along with the reason and date of early termination

The following will be considered as major protocol deviations:

- Major inclusionary/exclusionary deviations
- Missed visits/assessments such that a determination of healing status at both wound sites and ReCell donor site cannot be determined
- Significant protocol non-compliance that may confound evaluation of healing (e.g. use of inappropriate primary dressing)

Any significant deviations to the statistical analysis plan will be addressed in the final report for this study.

Randomization:

Allocation of treatments to the 2 defined wound regions at the INTEGRA™ MBWM treated wound sites will be done at random, using a computer generated randomization table provided by Glaser Consulting. Wound regions will initially be labeled “A” region and “B” region by the surgeon, and then an envelope will be opened which will indicate which treatment (ReCell or control) to assign to “A” region and which treatment to assign to “B” region. Randomization envelopes containing treatment region allocation will be opened in chronological order corresponding to subject enrollment.

Example Randomization Table

SUBJECT #	TREATMENT ASSIGNMENT
DERM- 001	A Region (ReCell) B Region (Control)
DERM- 002	A Region (ReCell) B Region (Control)

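### Exclusion item d in section 5.4 is inverted: it names a normal total bilirubin as the excluding result and does not itself exclude any value above 1.9 mg/dL

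*Combined protocol and SAP*

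**What the plan says.** The exclusion list in section 5.4 opens with "Subjects will not be eligible for study participation if they meet any of the following criteria". Its laboratory sub-list opens with "The subject has evidence of the following lab value results" and has seven items, a to g. Item d is "Bilirubin Total (serum) within upper limit of normal (normal range 0.3-1.9 mg/dL". The item after it, for comparison, is "Liver function test (AST/ALT) greater than 2 times upper limit of normal as defined by the clinical laboratory defined normal ranges".

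Section 5.5.4 applies the list as written: "Each subject must meet all inclusion and no exclusion criteria in order to qualify for receiving treatment using the ReCell device". A subject who has consented but does not meet the criteria is a screen failure. The same section requires the criteria to be verified again on the day of surgery, before the device kit is collected. Section 5.5.5 has outside monitors confirm that subjects entered meet the criteria.

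Section 5.7.3 counts "Major inclusionary/exclusionary deviations" among the major protocol deviations, without saying which eligibility deviations are major.

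**The concern.** An exclusion list works only if each item describes the result that should keep a subject out. Item d describes a normal result. It looks like an inclusion requirement moved into an exclusion list without being turned round.

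What is at stake is operational. The site must either fail subjects for having a normal bilirubin or enrol them against the written text. The protocol's introduction to study conduct allows no deviation without prior IRB approval, except to remove an immediate hazard, and section 6.4 requires deviations to be reported to the IRB. So a silent correction by site staff is not a clean solution. In addition, the one item that names bilirubin does not do what its neighbours do, which is to keep out subjects with an abnormal value.

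**Working it through.** No sample size, power or alpha enters this point. The check is a literal reading of item d, a comparison with its neighbours, a search for any other bilirubin rule, and one count.

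**1. Direction of the seven laboratory items (section 5.4).**

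| Item | Result that excludes | Kind of result |
|---|---|---|
| a. Hematocrit | 20% or lower | low |
| b. INR | above 1.8 | high |
| c. Creatinine | above 2.0 mg/dL | high |
| d. Total bilirubin | within the upper limit of normal, range 0.3 to 1.9 mg/dL | normal |
| e. AST/ALT | above 2 times the upper limit of normal | high |
| f. Albumin | below 2.0 g/dL | low |
| g. Platelets | below 70 K/µL | low |

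Six items exclude past an unfavourable threshold. Item d alone does not.

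**2. Literal application of item d to illustrative values.**

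- 0.3, 1.0 and 1.9 mg/dL meet item d, so the subject is excluded.
- 2.0 and 5.0 mg/dL do not meet item d, so it does not exclude the subject.

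**3. Does looser wording rescue it?** The phrase can be read in three ways:

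- at or below 1.9 mg/dL;
- inside 0.3 to 1.9 mg/dL;
- normal but near the upper limit.

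The first two exclude every value in the stated normal range. The third excludes only part of that range. None of the three excludes a value above 1.9 mg/dL.

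**4. Is it corrected elsewhere?** Bilirubin is named nowhere else in the documents. Sections 5.5.4 and 5.5.6 mention only a comprehensive metabolic panel. A character lost in reading the PDF is an unlikely explanation: item d is worded in prose, and the comparison signs of the neighbouring items survived.

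**5. Room for screen failures.** Section 5.3 allows up to 30 subjects to be consented for 20 evaluable, so 30 − 20 = 10 failures can be absorbed. The documents do not say what proportion p of consented subjects would have a normal bilirubin, so p is an assumption. On either of the first two readings, and with no other failures, at most 30 × (1 − p) subjects pass item d:

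- p = 1/3: 30 × 2/3 = 20
- p = 1/2: 30 × 1/2 = 15
- p = 2/3: 30 × 1/3 = 10
- p = 1: 30 × 0 = 0

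The target of 20 can be reached under the literal rule only if no more than 10/30, or one third, of consented subjects have a normal bilirubin.

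**The case against.** The strongest reply is that nobody will be misled. Six of the seven items exclude abnormal values, the intent of the seventh is plain, and staff will read it that way. That may well happen, and it lowers the chance that the literal rule ever stops enrolment. It does not make the written rule one that a monitor can audit, and the protocol gives the site no licence to apply a criterion as its opposite.

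Four stronger readings are tempting, and the documents do not support them.

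- **All 20 evaluable subjects would carry a major deviation.** Section 5.7.3 puts the word major in front of eligibility deviations and does not define it, so not every such deviation is major. Nor does any analysis consequence follow: the safety set takes all enrolled subjects, the effectiveness summaries remove nobody for a deviation, and no per-protocol set is defined.
- **The protocol offers no protection against a high bilirubin.** This is true of item d alone. A subject with a high value could still be kept out by the AST/ALT item, by the exclusion for concurrent conditions left to the investigator's opinion, or after the physician's review of screening results described in section 5.5.4.
- **The treatment comparison is biased.** Each subject is his or her own control, so an eligibility rule selects both regions together. The study is also, by section 5.7.2, a feasibility study without formal hypotheses.
- **Section 5.1 contains a second inversion.** It removes "areas with incomplete granulation, defined as a contiguous vascularized granulation layer at the" INTEGRA site from the study wound area. The direction is right, since poorly granulated areas are the ones removed. Only the definition is attached to the wrong term; sections 5.3 and 5.4 use it for successful engrafting. The note in the section 5.4 inclusion criteria states the exclusion of these areas correctly. This is a minor wording slip.

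**Conclusion.** The point holds. Item d is an operative eligibility rule that is wrong as written: it makes a normal total bilirubin an excluding result, does not itself exclude any value above 1.9 mg/dL, and runs opposite to the other six laboratory items.

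The size depends on how the site acts. Applied literally, it fails every screened subject within 0.3 to 1.9 mg/dL, and recruitment cannot reach 20 if more than one third of 30 consented subjects fall in that range. This assumes that the phrase covers the whole normal range; if it means only values near the upper limit, fewer subjects fail, but the direction is still wrong. If the item is ignored, each treated subject with a normal bilirubin has been enrolled against a written criterion, and whether that deviation is major is left open.

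No endpoint, estimate or within-subject comparison changes. The reason to correct it is that eligibility must be applied and audited as written.

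**What to change.** Amend item d so that it runs in the same direction as the other laboratory exclusions, with an abnormal rather than a normal bilirubin as the excluding result. The limit is for the investigators to set and state; none is proposed here. Check that any eCRF eligibility check agrees with the amended text. The sample eCRF (Appendix L) is not shown in the documents, so whether it carries the same wording is unknown.

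In the same amendment, reword the sentence in section 5.1 so that the definition describes complete granulation, in line with sections 5.3 and 5.4. The areas to be excluded do not change.

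The cost is a one-line change to item d, one reworded sentence in section 5.1, IRB approval of the amendment and, if needed, an edit to the eCRF check. No analysis or sample size changes.
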